#### 4.3.2.3. Progression/Reduction in Disease Symptoms

All the analyses below will be done on the ITT population with the same methodology as the analysis of time to clinical recovery in Section 4.3.2.2.

The analyses of time to defervescence, mild/absent cough, and mild/absent dyspnea will also be performed stratified by disease severity.

In addition to the specified analyses, all data will be provided via by-subject data listings.

##### 4.3.2.3.1. Respiratory Progression

The frequency of respiratory progression as assessed up to Day 29 will be tabulated by treatment group. Respiratory progression is defined as:

SpO2  $\leq 94\%$  on room air or PaO2/FiO2 < 300 mmHg, and

- a. Requirement for supplemental oxygen, or
- b. More advanced ventilator support

The treatment effect will be analyzed via generalized linear mixed models using SAS PROC GLIMMIX, with respiratory progression (Yes/No) as the dependent variable, and treatment group, disease severity, age (in years), and visit as independent variables. Least-squares means of the treatment group effect on the logit scale (difference on the log odds) will be presented, along with a 90% CI and a descriptive p-value from a two-sided alpha-level test.

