 - i. Fever ≤ 37.2 °C oral,
 - ii. Respiratory rate ≤ 24 /minute on room air,
 - iii. Oxygen saturation SpO2 > 94% on room air,
 - iv. Cough mild or absent on a patient reported scale of severe, moderate, mild, absent.
- 3. Clinical effect as measured by the National Early Warning Score 2 (NEWS2) system.
- 4. All-cause mortality as assessed daily up to 29 days and at final follow up on Day 60.
- 5. Frequency of respiratory progression as assessed up to 29 days (daily and per SOC at each site) and defined as:
 - a. SpO2 \leq 94% on room air or PaO2/FiO2 \leq 300mmHg, and
 - b. requirement for supplemental oxygen, or
 - c. more advanced ventilator support.
- 6. Time to defervescence (in those with fever at enrollment) as assessed daily up to 29 days and at Day 60 (if possible).
- 7. Time to cough reported as mild or absent (in those with cough at enrollment rated severe or moderate) as assessed daily up to 29 days and on Day 60.
- 8. Time to dyspnea reported as mild or absent (on a scale of severe, moderate, mild absent, in those with dyspnea at enrollment rated as severe or moderate) as assessed daily up to 29 days and on Day 60 (if possible).
- 9. Frequency of requirement for supplemental oxygen or non-invasive ventilation as assessed daily up to 29 days and on Day 60.
- 10. Time to SARS-CoV-2 RT-PCR negative in upper respiratory tract specimen as assessed up to 29 days.
- 11. Change in SARS-CoV-2 viral load in upper respiratory tract specimen as assessed by area under viral load curve as assessed up to 29 days.
- 12. Frequency of requirement for mechanical ventilation as assessed up daily to 29 days and at Day 60
- 13. Safety of favipiravir + SOC v. SOC alone as assessed daily up to 29 days and at Day 60.
- 14. C-reactive protein (CRP) over time.
- 15. Population PK analysis of favipiravir with assessment of maximum plasma concentration (C_{max}), minimum plasma concentration (C_{min}), and AUC_(0-24h) on Days 1, 2, 8 and 14.

Study Sites	Approximately 8 sites in the U.S.A.
Planned Enrollment	Approximately 50 subjects; randomized 1:1
Study Population	Adults who are hospitalized for treatment of confirmed COVID-19

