### 1.2.2. Randomization Methodology

Subjects will be evaluated for eligibility during Day 1, prior enrollment in the study or starting treatment. The randomization procedure will be performed centrally using the electronic data capture (EDC) system, IBM Clinical Development.

Approximately 50 subjects are planned to be randomized at a 1:1 ratio to receive either favipiravir + SOC or SOC alone. Randomization will be stratified by site and severity of illness at enrollment. Severity of illness at enrollment will be graded (i.e., critical disease, severe disease, or mild/moderate disease) as follows:

- Critical disease:
  - Requires supplemental oxygen delivered by non-rebreather mask or high-flow cannula, OR
  - Requires use of invasive or non-invasive ventilation, OR
  - Requires treatment in an intensive care unit, use of vasopressors, extracorporeal life support (i.e., extracorporeal membrane oxygenation [ECMO]).
- Severe disease:
  - Evidence of pneumonia on chest x-ray or computed tomography (CT) scan, or chest auscultation (rales, crackles), OR
  - Peripheral capillary oxygen saturation ( $SpO_2$ )  $\leq$  93% on room air OR partial pressure of oxygen ( $PaO_2$ )/fraction of inspired oxygen ( $FiO_2$ )  $<$  300 mmHg, OR
  - Requires supplemental oxygen by nasal canula, simple face mask, or other similar oxygen delivery device.
- Mild/moderate disease:  $SpO_2 > 94\%$  and respiratory rate  $\leq 24$  breaths/min without supplemental oxygen

The randomization will target balance within stratum. This does not guarantee balance overall; however, utilizing a block size of 2, as well as with sufficient sample size within strata, balance will be approximately maintained while pooling across sites.

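### Respiratory progression is defined as a state rather than a change from entry, so a treatment difference on it cannot be read as prevention of worsening

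*SAP*

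**What the plan says.** **Definition.** SAP 4.3.2.3.1 sets an oxygenation condition (SpO2 at or below 94% on room air, or PaO2/FiO2 below 300 mmHg) and adds either "Requirement for supplemental oxygen, or" or "More advanced ventilator support". Protocol Synopsis, secondary endpoint 5, "Frequency of respiratory progression as assessed up to 29 days", has the same elements, including "requirement for supplemental oxygen, or" advanced ventilator support. It sets PaO2/FiO2 at or below 300.

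**Analysis.** Two outputs are planned in SAP 4.3.2.3.1. The first is descriptive: "The frequency of respiratory progression as assessed up to Day 29 will be tabulated by treatment group". The second is a generalized linear mixed model of a Yes/No outcome, with treatment "group, disease severity, age (in years), and visit as independent variables". There is no term for oxygen use or endpoint status at baseline.

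**Analysis set.** SAP 4.3.2.3 states "All the analyses below will be done on the ITT population", and adds that the methodology follows that of time to clinical recovery.

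**Who enters.** One of the alternative criteria for the severe stratum in SAP 1.2.2 is "Requires supplemental oxygen by nasal canula, simple face mask, or other similar oxygen delivery device". The critical stratum includes subjects on non-rebreather or high-flow oxygen. Mild/moderate subjects have SpO2 above 94% without oxygen. Protocol 5.2 excludes subjects on a ventilator at entry.

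**The concern.** Progression ordinarily means that a subject got worse. Under this rule a subject admitted with low saturation on nasal oxygen meets the definition on arrival and continues to meet it while being weaned. A subject who steps up from oxygen to ventilation was already counted, so the step adds nothing to the tabulated frequency.

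Neighbouring endpoints handle entry status explicitly. Defervescence, cough and dyspnea (SAP 4.3.2.3.2 to 4.3.2.3.4) are limited to subjects with the symptom at entry or within 72 hours. Respiratory progression has no matching limit to subjects who could still have the event.

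What is at stake is interpretation. The trial is meant to inform endpoint choice for a confirmatory study (Protocol Synopsis and 9.1). Fewer progressions on favipiravir could reflect faster weaning or chance differences in entry status with no worsening prevented. A real effect on worsening could be largely hidden.

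**Working it through.** The documents give no rate, effect size or power for this endpoint, so there is no planned figure to reproduce. From Protocol 9.2 I take 25 per arm and two-sided alpha 0.10. Everything else below is assumed.

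**1. Tabulated frequency.** Let b be the share meeting the definition at entry and p the risk of new worsening in the rest. If every entry-positive subject is counted, the ever-positive frequency is F = b + (1 − b)p. The treatment difference therefore shrinks by the factor (1 − b). Assume p = 0.40 on SOC and 0.15 on favipiravir, a true difference of 25 points:

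| b | SOC | Favipiravir | Difference |
|---|---|---|---|
| 0.50 | 0.50 + 0.50 × 0.40 = 70% | 0.50 + 0.50 × 0.15 = 57.5% | 12.5 points |
| 0.70 | 0.70 + 0.30 × 0.40 = 82% | 0.70 + 0.30 × 0.15 = 74.5% | 7.5 points |
| 0.85 | 0.85 + 0.15 × 0.40 = 91% | 0.85 + 0.15 × 0.15 = 87.25% | 3.75 points |

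With p = 0.30 v 0.10 the pattern is the same: b = 50% gives 65 v 55% and b = 70% gives 79 v 73%. The odds ratios are 0.66 and 0.72, against 0.26 among subjects free of the state at entry.

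**2. Power of a simple comparison of those frequencies** (two proportions, normal approximation, p = 0.40 v 0.15). As written, power is 23%, 16% and 11% for b = 50%, 70% and 85%, or 24%, 17% and 13% counting both tails. Worsening from baseline would have 64% power if all 25 per arm carried the 40% v 15% risk, including subjects already on oxygen. If only entry-negative subjects are at risk, n = 25(1 − b) = 12.5, 7.5 and 3.75 per arm, and power is about 40%, 28% and 19%.

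**3. The by-visit model.** Here a weaned subject becomes No at later visits, so step 1 does not describe it. It was simulated with a GEE in place of the mixed model, adjusted for severity and visit. Assumptions: strata 20/60/20 (mild-moderate/severe/critical), with 0%, 70% and 100% positive at entry, so 0.60 × 0.70 + 0.20 × 1.00 = 62% overall.

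| Scenario | Odds ratio | Rejections at 0.10, N = 50 |
|---|---|---|
| Faster recovery only (median 8 v 5 days on oxygen) | 0.67 | 22% |
| Less new worsening only (30% v 10%) | 0.85 | 14% |
| Both | 0.54 | 36% |
| Neither | 1.02 | 11% |

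Under these assumptions the model responds more to weaning than to prevented worsening, and it detects the worsening-only effect barely more often than it rejects under no effect.

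**The case against.** A reader might infer that the endpoint simply measures baseline prevalence and can show nothing about worsening. The documents do not support that. Mild/moderate subjects are free of the state at entry. Severe subjects can qualify on pneumonia alone and may also be free of it. Both groups can contribute true new events. The definition needs low SpO2 or PaO2/FiO2 as well as oxygen, so the entry-positive share may be below the share on oxygen. The planned test is also a by-visit model in which weaned subjects stop being events, not a comparison of ever-positive proportions. All of this stands. It turns the criticism from a fixed outcome into a mixed one, and it means that the power figures in step 2 do not describe the planned test.

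Other defences are weaker:

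- **Severity adjustment** absorbs part of the entry difference but cannot turn a state into a change. The severe stratum itself mixes subjects with and without oxygen.
- **The words "More advanced ventilator support"** suggest escalation, but no comparator is named, and the oxygen limb alone is enough.
- **Other analyses** cover some of the ground. Mechanical ventilation or ECMO (SAP 4.3.2.5) should be almost wholly new after entry, and the 6-point scale (4.3.2.1) and mortality (4.3.2.7) are analysed. None isolates new oxygen need or a move from low-flow to high-flow support. The baseline-referenced analysis in 4.3.2.1.1 pools decline with no change.

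Finally, SAP 3.2 makes p-values other than the primary descriptive only. That limits the consequence but leaves the definition as it is.

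**Conclusion.** The point holds in this form: as written, subjects already hypoxic and on oxygen at entry can count as progressed without deteriorating, so a treatment difference is not evidence that worsening was prevented. This follows from the text and needs no assumed numbers.

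The size of the dilution is not known. The frequencies of 70 v 58%, 82 v 75% and 91 v 87% rest on assumed worsening risks and entry shares. The difference approaches zero only when nearly everyone is positive at entry; at 50% half of it survives. The 64% power comparator should not be cited without its condition that subjects already on oxygen carry the same step-up risk. A better definition repairs the meaning of the endpoint but does not make 50 subjects adequate for it.

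The endpoint is secondary and descriptive, so the change is advisable and the primary conclusion is unaffected.

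**What to change.** Define progression once per subject, by Day 29, as worsening from baseline in respiratory support: new onset of the state in a subject not meeting it at entry, or an increase of at least 1 point on the 6-point scale, which includes death. SAP 4.3.1 already uses that 1-point increase as its meaning of worsening, for censoring. Analyse it as one binary outcome by treatment and disease severity, and say how subjects with incomplete follow-up to Day 29 are classified. The as-written state analysis can stay as supportive, labelled as need for oxygen or support over time.

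Also reconcile:

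- the PaO2/FiO2 limit (at or below 300 in the Protocol, below 300 in the SAP);
- the and/or grouping, since the Protocol's list can be read as letting advanced ventilator support qualify on its own;
- the time-to-clinical-recovery methodology invoked in SAP 4.3.2.3 with the mixed model in 4.3.2.3.1. Recovery's restriction to subjects abnormal at baseline or within 72 hours would aggravate the problem if carried over.

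**Cost.** No new data: 6-point status is recorded daily in hospital and at visits. The change departs from Protocol secondary endpoint 5, so it must be listed in SAP Section 5. The scale does not register increases in oxygen flow within a category.

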| ECOG Performance
Status                               | X                 |   | X     | X     | X     | X      | X      | X                                       | X                  | X   |  |
| Study Specific
Symptom Status                         | X                 |   | X     | X     | X     | X      | X      | X                                       | X                  | X   |  |
| Randomization  | X                 |   |       |       |       |        |        |   |                    |   |  |
| Investigational Product
Dosing                                    |                   | Favipiravir Dosing Days 1-14
(1800mg BID on Day 1000mg BID Days 2-14)  |       |       |       |        |        |   |                    |   |  |
| Solicitation of
Treatment-Emergent
Adverse Events  |                   | X   | X     | X     | X     | X      | X      | X                                       | X                  | X   |  |
| Release from the Study   |                   |   |       |       |       |        |        |   |                    | X   |  |

1. Hematology, Chemistry (See Protocol Section 8.4).
2. May use results of labs taken at the hospital as part of SOC if done no more than 24 hours prior.
3. To be measured every day while hospitalized and at each clinic visit after hospital discharge through Day 60
  - a. Vital signs
  - b. Clinical Status 6-point scale
  - c. NEWS2
  - d. ECOG Performance status
  - e. Study-specific symptom status
  - f. Adverse Events
  - g. SpO2
  - h. Limited PE (heart and lungs)
4. PK on Day 1 prior to favipiravir dosing and between 45 to 75 minutes post-first dose.

5. PK trough samples to be taken approximately 30 minutes prior to any dose.
6. PK peak samples to be taken between 45 and 75 minutes post-dose.
7. Maintenance dose for CP score A is 800mg BID.
8. Days 45 and 60 may be completed in the hospital, outsubject clinic or by phone.
9. Subjects will undergo 9 planned venipunctures.
10. To be completed by PI or designee.
11. Days 3, 8, 11 Nasopharyngeal and Oropharyngeal Swabs for Viral RNA, PCR, and TCID50 may be done +/- 1 day from their scheduled day. Swabs will also be obtained on day of discharge from hospital if discharge occurs before Day 15.
12. To be checked throughout hospitalization and at clinic visits and changes only recorded as applicable.

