## 3.11. Visit Windows

It is expected that all visits should occur according to the protocol schedule. However, analysis visits will be derived based on study day for all by-visit summaries and analyses. Analysis visit designations are detailed in [Table 3-1](#).

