**Table 3-1 Post-Baseline Analysis Visit Designations**

| Analysis Visit | Analysis Visit Range |
|-----------------------|-----------------------------|
| Day 1                 | Day 1                       |
| Day 2                 | Day 2                       |
| Day 3                 | Days 3-5                    |
| Day 8                 | Days 6-9                    |
| Day 11                | Days 10-12                  |
| Day 15                | Days 13-17                  |
| Day 21                | Days 18-24                  |
| Day 29                | Days 25-33                  |
| Day 45                | Days 34-52                  |
| Day 60                | Days 53-70                  |

In the event there are multiple assessments within a given analysis range, the value closest to the target day (understood to be the day identified in the analysis visit) will be chosen. If more than one measurement are the same distance from the target day, the earlier visit will be chosen.

In data listings, the relative day of all dates will be presented.

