#### 4.3.2.5. Reduction in Oxygen/Ventilation Requirements

The frequency of requirement for any supplemental oxygen or ventilation (non-invasive, mechanical, or ECMO), as assessed daily up to 29 days and on Day 45 and 60, if possible, will be analyzed in a similar fashion as respiratory progression in [Section 4.3.2.3.1](#).

In addition, the frequency of requirement for any ventilation requirement (non-invasive, mechanical or ECMO) and either mechanical ventilation or ECMO will be analyzed in the same manner as above.

The analyses on oxygen/ventilation requirements will be performed using the ITT population.

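### Read literally, the visit-window rule gives the respiratory progression and oxygen/ventilation models one nearest-day record per visit, so short episodes between those days miss the modelled treatment effect

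*SAP*

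**What the plan says.** **Endpoint.** The Protocol Synopsis lists as secondary endpoint 5 the "Frequency of respiratory progression as assessed up to 29 days (daily and per SOC at each site"). Secondary endpoints 9 and 12 (oxygen or non-invasive ventilation, and mechanical ventilation) are likewise daily to Day 29, with a further assessment at Day 60.

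**Collection.** SpO2, vital signs and the 6-point scale carry this footnote in SAP Table 1-1: "To be measured every day while hospitalized and at each clinic visit after hospital discharge through Day 60".

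**Model.** SAP 4.3.2.3.1 tabulates the frequency of respiratory progression up to Day 29. It then estimates the treatment effect by GLIMMIX, "with respiratory progression (Yes/No) as the dependent variable, and treatment group, disease severity, age (in years), and visit as independent variables". SAP 4.3.2.5 says that oxygen or ventilation need, "as assessed daily up to 29 days and on Day 45 and 60, if possible, will be analyzed in a similar fashion as respiratory progression".

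**Record selection.** SAP 3.11 states that "analysis visits will be derived based on study day for all by-visit summaries and analyses". Under Table 3-1, when a window holds several assessments, "the value closest to the target day (understood to be the day identified in the analysis visit) will be chosen", and ties go to the earlier one. No exception is made for these two sections.

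**The concern.** The endpoints concern what happens on any day up to Day 29, and daily inpatient data are collected for that purpose. If the model sees only the record nearest each target day, its odds ratio describes status on a handful of days. A brief deterioration that starts and resolves between two kept days is scored No at both neighbouring visits.

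An effective drug might prevent or shorten such episodes. The GLIMMIX model is also the only source of a treatment estimate, confidence interval and p-value for whether these events occur. For respiratory progression, the model and the Day 29 tabulation could then disagree on the same endpoint. The trial is meant to inform the choice of Phase 3 endpoints, so the estimate should match its definition.

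**Working it through.** The plan states no figure on this point. Its one design calculation, 50 subjects for the primary log-rank test, does not bear on it. The check applies the written rule to daily inpatient records.

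**Inputs (SAP Table 3-1, to Day 29).** Target day and window: 1 (1), 2 (2), 3 (3-5), 8 (6-9), 11 (10-12), 15 (13-17), 21 (18-24), 29 (25-33).

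**Step 1: days kept.** With a record every day, the nearest record is the target day itself.
- Stay to Day 29: Days 1, 2, 3, 8, 11, 15, 21 and 29 are kept, 8 of 29. Unused: 21/29 = 72%.
- Stay to Day 15: Days 1, 2, 3, 8, 11 and 15 are kept, 6 of 15. Unused: 9/15 = 60%.

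**Step 2: gaps between kept days.** For a stay to Day 29 the gaps are Days 4-7 (4 days), 9-10 (2), 12-14 (3), 16-20 (5) and 22-28 (7). For a stay to Day 15 only the first three apply.

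**Step 3: share of episodes missed.** An episode of L days is missed only if it fits inside a gap. A gap of g days holds max(0, g - L + 1) such start days. A stay of S days allows S - L + 1 start days in all, taken as equally likely. Then:

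share missed = [sum over gaps of max(0, g - L + 1)] / (S - L + 1)

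For L = 3 and S = 29: (2 + 0 + 1 + 3 + 5)/27 = 11/27 = 41%.
For L = 3 and S = 15: (2 + 0 + 1)/13 = 3/13 = 23%.

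| Episode length | Stay to Day 29 | Stay to Day 15 |
|---|---|---|
| 1 day | 21/29 = 72% | 9/15 = 60% |
| 2 days | 16/28 = 57% | 6/14 = 43% |
| 3 days | 11/27 = 41% | 3/13 = 23% |
| 5 days | 4/25 = 16% | 0/11 = 0% |
| 7 days | 1/23 = 4% | 0/9 = 0% |
| 8 days | 0/22 = 0% | 0/8 = 0% |

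The longest gap is 7 days, so no inpatient episode of 8 days or more can be missed.

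**Step 4: one example.** A subject needs non-invasive ventilation on Days 5 and 6 only. Day 5 lies in the Day 3 window, where the Day 3 record is used: No. Day 6 lies in the Day 8 window, where the Day 8 record is used: No.

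Episode length is an assumption shown as a range. The documents give neither a length nor an event rate, so the effect on the odds ratio or on power cannot be computed.

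**The case against.** The strongest reply is that the SAP never says how the yes/no value at each visit is formed, so tying the window rule to GLIMMIX is a reading of the text.
- SAP 4.3.2.5 speaks of daily assessment, and SAP 1.2.6.1 collects periods of respiratory assistance, so an any-day-in-window derivation is open.
- The 4.3.2.3.1 model reports one overall treatment effect without a visit-by-treatment term, unlike the longitudinal model in 4.3.2.1.
- The opening of 4.3.2.3 applies the time-to-recovery methodology to everything beneath it, which does not fit GLIMMIX.

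This stands in part. The reading is still the literal one: visit is a model term, the window rule covers all by-visit analyses, and no exception is written. Where the SAP wants a worst or maximum value it says so, for laboratory shift tables (4.5.3) and daily viral load (4.3.2.9).

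A reader might infer that events on other days are never counted. The documents do not support that. An episode that touches a kept day is counted, the Day 29 tabulation is not restricted to visits, and the ANCOVA in SAP 4.3.2.6 uses exact durations of support. The duration analysis does answer a different question, mean days of support.

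A reader might also infer that about half of 3-day episodes are lost. That needs every episode to start on Day 4 or later in a stay to Day 29 (11/24 = 46%). Protocol 9.6 expects some discharges before Day 15.

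Finally, the protocol speaks of frequency and does not define an ever/never outcome per subject. SAP 3.2 makes all p-values other than the primary descriptive. Both points are fair and limit the severity.

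**Conclusion.** The concern holds in a limited form. Followed as written, the window rule removes from these models any episode lying wholly between kept days. At a stay to Day 29 the loss is substantial for episodes of one to three days (72% to 41%), small by seven days and nil from eight. At a stay to Day 15 it is 60% to 23% for one to three days and nil from five.

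The figures assume daily inpatient records, a uniformly distributed start day and the literal reading of SAP 3.11. After discharge, records are sparser and the one kept may not fall on the target day.

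No decision rule rests on these models. The primary analysis is unaffected, and other planned outputs can still see the missed days. This is a cheap improvement to make before analysis and does not threaten the trial's main conclusion.

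**What to change.** 1. In SAP 3.11, exempt respiratory progression and oxygen/ventilation need from the closest-value rule. In 4.3.2.3.1 and 4.3.2.5, score a window Yes if the criterion is met on any day in it. The Table 3-1 windows are contiguous, so each inpatient day falls in exactly one. The last of these runs to Day 33, so cap it at Day 29 for the endpoints defined to that day.

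2. Add a per-subject analysis: new or worsened need relative to baseline on any post-baseline day to Day 29, and at Day 60 where the protocol says so. Use logistic regression with treatment, disease severity and the SAP's age covariate. The comparison with baseline is essential. Under SAP 1.2.2, severe or critical subjects may already be on oxygen or non-invasive ventilation at entry. A rule of ever meeting the criterion from time zero would count them as events before treatment could act.

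3. State how death and the sparser records after discharge are handled, and reconcile the opening of 4.3.2.3 with the GLIMMIX specification.

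**Cost.** SAP wording and modest programming, with no new data. Two drawbacks should be acknowledged: a window with more daily records has more chance of a Yes, and the per-subject analysis shows no by-visit pattern, which the windowed model still supplies.
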